7.7 Final FOLLOW-UP at D90 (3 months)

The study has a final follow up at D90 (3 months) for assessment of the final outcome, need of organ support (mainly hemodialysis), and use of health care services. Modified ranking scale (mRS) at D90 will be used to evaluate study subject disability. Data will be gathered from patient charts, national databases or by phone directly from the patient or a health care facility. If a patient is on hemodialysis at D90, it is considered as permanent in this study. Acute renal failure related to RAAA often resolves within 3 months if it is reversible.

If the patient refuses any of the above assessments or is lost to follow-up, this is noted in the eCRF.

8 STATISTICAL METHODS

Detailed information regarding statistical methods will be provided separately in the Statistical Analysis Plan (SAP). Any deviations from the planned analyses specified within the SAP will be justified in writing and presented within the final clinical study report.

8.1 Populations for analysis

The following analysis sets will be defined for statistical analysis:

The Full Analysis Set for Efficacy (FAS-E) consists of all randomised patients receiving study treatment but excluding the early deaths (within 36 hours from first dose of the study treatment) and comprises the analysis set on which the primary efficacy analysis is based.

The Per Protocol Set (PPS) consists of the patients in the FAS excluding patients with major protocol violations. A relevant list of the major protocol violations will be detailed in the SAP. The precise definition of the PPS at the patient level will be identified at the blind review conducted both before interim and final analysis.

Statistical analyses for the primary and secondary endpoints are performed on both the FAS-E and PPS.

The Full Analysis Set for Safety (FAS-S) consists of all randomised patients receiving study treatment and comprises the analysis set on which the evaluation of safety is based. A patient receiving the wrong treatment according to the randomisation will be analysed for safety and tolerability in the treatment group corresponding to the treatment received.

8.2 Sample size estimation

The primary efficacy endpoint is all cause mortality at D30. Death within 36 hours from the first dose of the study treatment leads to exclusion from efficacy analysis (see section 8.5.1 Efficacy Analysis).

A sample size of 129 eligible patients for the primary efficacy analysis, with a 2:1 ratio to active (86) and placebo (43), will detect the difference of 22% between the two treatment groups with 80 % power using 2-sided test with 0,05 significance level. Because of the planned interim analyses, the calculations assume that 2 sequential tests are made and the O'Brien-Fleming spending function is used to determine the test boundaries.

Power calculation assumes 37 % proportion of events on placebo group and 15 % proportion for the active treatment group.

To achieve a sample size of 129 for the primary efficacy analysis, taking account the estimated amount of early deaths within 36 hours from first dose of the study treatment (estimated 15 %), there should be 152 patients randomised to the study.

The sample size calculations will be re-evaluated after the interim has been performed (comprising at least 31 eligible patients for the primary efficacy analysis).

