1.1 Disease review and rationale for the study

Ruptured abdominal aortic aneurysm (RAAA) is a surgical emergency with an overall mortality of 70–80 % (Bown et al. 2002). It requires immediate surgery and aortic repair. Approximately half of RAAA patients do not reach the hospital and despite immediate surgery and intensive care treatment another half of the patients die in hospital within 30 days post-operatively mostly due to multi-organ failure. Surviving RAAA patients have a long-life expectancy comparable to that of their age group (Alric et al. 2003, Korhonen et al. 2003 and Biancari et al. 2011). The cause of high post-operative mortality is in part due to prolonged hypotension from the ruptured aorta and the aftermath of restoring blood flow; reperfusion, vascular leakage and failure of vital organs. Diagnosed primary causes of post-operative mortality are acute renal failure, intestinal infarction, myocardial infarction, respiratory insufficiency and multi-organ failure (Bown et al. 2004).

Despite several decades of RAAA surgery and advancements in modern medicine surprisingly little has been achieved in reducing post-operative mortality (Bown et al. 2001 and Vänni et al. 2016). A major advancement benefiting the patients has been the minimisation of the time of hypotension, i.e. the time from rupture to clamping of the aorta. For several decades intra-operative mortality has remained rather small and constant, at around 3,5 %. Post-operative mortality has shown a slight decline over the decades but still remains high at around 25–50 % depending on patient cohorts. Recently very significant publications have been made on the mortality of RAAA, because endovascular aortic repair (EVAR) has been suggested a promising treatment without major surgical trauma and lower mortality. Open and endovascular aortic repair for a rupture (rEVAR) have been studied against each other in both prospective randomized settings and registry based studies, but no clear significant difference has been seen in mortality rates (IMPROVE trialists 2014 and Karthikesalingam et al. 2014). Thus, we can now state that due to the overall haemorrhagic shock and ischemia-reperfusion injury leading to a systemic inflammatory response syndrome (SIRS) and multi-organ failure (MOF) the mortality of RAAA is very precisely around 30-35%, which also applies to Finland (Kantonen et al. 1999, Biancari et al. 2011 and Vänni et al. 2016).

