 19.4 Data listing plan24

1 Abbreviations

AE	Adverse event
ANOVA	Analysis of variance
ATC	Anatomical Therapeutic Chemical
FAS-E	Full analysis set for efficacy
FAS-S	Full analysis set for safety
IAP	Intra-abdominal pressure
ICU	Intensive care unit
MedDRA	Medical dictionary of regulatory authorities
mRS	Modified ranking scale
NAb	Neutralizing antibody
PD	Pharmacodynamics
PIM	Potential Inflammatory Markers
PPS	Per protocol set
SD	Standard deviation
SAE	Serious adverse event
SOFA	Sequential organ failure assessment
TEAE	Treatment emergent adverse event
VFD	Ventilator free day

2 General remark

This SAP version further details the SAP dated 17.6.2019, which was generated before performing the Interim analysis for the 35 evaluable patients. Study was discontinued after the Interim analysis. The earlier version of the SAP concentrated on the primary analyses and this version will entail all planned analyses. The analysis plans concerning the primary analyses are not changed from the previous version.

As the study was discontinued, analyses described here, will be performed on the available data gathered thus far.

3 Study objective(s)

The primary objective of this study is to evaluate the safety and the efficacy of FP-1201-lyo over placebo on all-cause mortality at study day 30; D30 (30 days from the first dose of study medication).

The secondary objectives of this study are

1. To evaluate the efficacy of FP-1201-lyo treatment by assessing short term outcomes (D30) and mid-term outcomes (D90 [3 months])
2. To evaluate the safety and tolerability of FP-1201-lyo treatment

3. To evaluate the pharmacodynamics (PD) of FP-1201-lyo
4. To evaluate the Tentative Disease Specific Marker CD73 and Potential Inflammatory Markers (PIM) IL-6 and HGF
5. To evaluate neutralizing antibodies against IFN beta-1a (NAbs)

4 Design and type of the study

This is a multicentre, randomised, double-blind, Phase II, parallel group comparison study of the efficacy and safety of FP-1201-lyo compared to placebo in patients surviving emergency open surgery for an infra-renal ruptured abdominal aortic aneurysm. Both treatment groups will receive standard supportive care.

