- Length of hospital stay, in terms of hospital free days at D90
- Length of stay at another health care facility at D90
- Length of haemodialysis needed

6 Sample size considerations

The primary efficacy endpoint is all cause mortality at D30. Death within 36 hours from the first dose of the study treatment leads to exclusion from efficacy analysis. A sample size of 129 eligible patients for the primary efficacy analysis, with a 2:1 ratio to active (86) and placebo (43), will detect the difference of 22% between the two treatment groups with 80 % power using 2-sided z-test with 0.05 significance level. To take account of the planned interim analysis, calculations assume that 2 sequential tests are made (in addition to final analysis) and the O'Brien-Fleming spending function is used to determine the test boundaries. Statistical analysis plan for the interim analyses will be presented in a separate document.

Power calculation assumes 37 % proportion of events on placebo group and 15 % proportion for the active treatment group.

To achieve a sample size of 129 for the primary efficacy analysis, taking account the estimated amount of early deaths within 36 hours from first dose of the study treatment (estimated 15 %), there should be 152 patients randomised to the study.

Study was discontinued after the first Interim analysis. Therefore, the sample size did not reach the 129 patients aimed for.

7 Statistical hypotheses

The primary objective of this study is to evaluate the safety and the efficacy of FP-1201-lyo over placebo on reducing all-cause mortality at study day 30, i.e., the null-hypothesis to be tested is

H_0 : FP-1201-lyo is not superior to control with respect to all-cause mortality at study day 30

against

H_1 : FP-1201-lyo is superior to control with respect to all-cause mortality at study day 30

8 Analysis datasets

Statistical analyses will be performed on the following analysis datasets.

The Full Analysis Set for Efficacy (FAS-E) consists of all randomised patients receiving study treatment but excluding the early deaths (within 36 hours from first dose of study treatment) and comprises the analysis set on which the primary efficacy analysis is based.

The Per Protocol Set (PPS) consists of the patients in the FAS-E excluding patients with major protocol violations possibly affecting the primary study endpoint analysis.

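### Does the 37% placebo mortality behind the sample size conflict with the mortality figures in the protocol's introduction?

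*Protocol*

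**What the plan says.** Protocol 8.2 and SAP 6 give the same planning rates: "Power calculation assumes 37 % proportion of events on placebo group and 15 % proportion for the active treatment group". They apply to 129 evaluable patients, 86 active and 43 placebo, with 80% power at two-sided 0.05 and O'Brien-Fleming spending. Protocol 8.2 also states: "Death within 36 hours from the first dose of the study treatment leads to exclusion from efficacy analysis". The 129 is raised to 152 randomised by allowing 15% for early deaths. Neither section cites a source for the 37%.

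Protocol 1.1 offers three mortality figures:

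- "another half of the patients die in hospital within 30 days post-operatively"
- post-operative mortality that "still remains high at around 25–50 % depending on patient cohorts"
- a closing statement that "the mortality of RAAA is very precisely around 30-35%, which also applies to Finland"

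Protocol 8.2 and 8.6 provide for the sample size to be re-evaluated after the first interim. Section 8.6 adds a blind data review before the interim to check assumptions such as the overall number of events. SAP 2 says that its previous version was "generated before performing the Interim analysis for the 35 evaluable patients" and that the study was then discontinued. SAP 6 adds: "Therefore, the sample size did not reach the 129 patients aimed for".

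**The concern.** The 37% is conditional on surviving 36 hours, and neither document says so in those words. Once the early deaths are put back, the implied placebo mortality is well above the 30-35% on which Protocol 1.1 ends. If the lower figure were the right one for this population, fewer deaths would be expected. At the same relative risk or odds ratio, 129 patients would then give less than the stated power. A reader of the stopped trial might also blame low power on early termination alone when a lower control rate could have contributed.

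**Working it through.** **Inputs.** From Protocol 8.2: 37% and 15% among evaluable patients, 43 and 86 patients, 15% early deaths, 152 randomised. From Protocol 1.1: about half, 25-50% and 30-35%. Assumption: early deaths are equally frequent in both arms, since no rate by arm is given.

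**Reproducing the plan.** For a two-proportion z-test, power = Φ[(d − 1.96 × SE₀) / SE₁], with SE₀ pooled and SE₁ unpooled.

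- Pooled rate: (43 × 0.37 + 86 × 0.15)/129 = 0.2233
- SE₀ = √[0.2233 × 0.7767 × (1/43 + 1/86)] = 0.0778
- SE₁ = √[0.37 × 0.63/43 + 0.15 × 0.85/86] = 0.0831
- Power = Φ[(0.22 − 1.96 × 0.0778)/0.0831] = Φ(0.813) = 79.2%

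Exact enumeration of the same test gives 79.7%. A group-sequential calculation with O'Brien-Fleming-type spending at 31, 84 and 129 patients, using the pooled variance, gives 80.0%. For enrolment, 129/0.85 = 151.8, so 152. The stated figures are internally correct.

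**Total mortality implied.**

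- Placebo: 0.15 + 0.85 × 0.37 = 46.45%
- Active: 0.15 + 0.85 × 0.15 = 27.75%

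The 46.45% is inside 25-50%, just below one half, and 11 to 16 points above 30-35%.

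**Power if 30-35% were the relevant rate.** Planned relative risk: 0.15/0.37 = 0.405. Planned odds ratio: (0.15/0.85)/(0.37/0.63) = 0.300. If 30-35% is total mortality, the evaluable rate is (total − 0.15)/0.85, which is 17.6% at 30% and 23.5% at 35%.

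| Reading of 30-35% | Relative risk held | Odds ratio held | 22 points held |
|---|---|---|---|
| Total mortality (evaluable 17.6-23.5%) | 45-57% | 54-64% | impossible at 17.6%; 96% at 23.5%, but needs 1.5% active mortality |
| Rate among 36-hour survivors | 68-76% | 73-78% | 88% (30% v 8%) to 81% (35% v 13%) |

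Holding the active rate at 15% instead gives 6-23% on the total-mortality reading and 52-73% on the survivor reading. If one half is total mortality, the evaluable rate is 41.2%. Power is then 85% with the relative risk held, 82% with the odds ratio held and 75% with 22 points held.

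**What the stopped trial could show.** At 35 evaluable patients, power is 32% on the planned rates. At 30-35% total mortality it is 18-26% across the relative-risk and odds-ratio versions. Expected deaths are 35 × 0.2233 = 7.8 as planned, against 3.5 to 5.0 at 30-35% total. Eight deaths in 35 have an exact 95% interval of 10-40%. That covers the planned pooled rate of 22.3% and almost all of the 9.9-14.2% expected under the lower control rate.

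**The case for a change.** The best case for a change does not need the 15% allowance. Even with no early deaths, 37% exceeds 35%, and any early deaths widen the gap. With the relative risk or odds ratio held, every computed version of 30-35% falls below 80%. The 22-point difference rescues power only if active mortality is 8-13%, better than the planned 15%. Planning to re-evaluate the sample size does not supply a source for the 37%. The SAP, completed after the trial stopped, repeats 37% and 15% and reports no result of the blind check of event numbers. A citation and a short table would cost little.

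Some of this stands: the 37% is uncited and is not tied to any figure in Protocol 1.1. The rest does not show an error. The 30-35% sentence follows a comparison of open and endovascular repair and speaks of ruptured aneurysm generally, whereas this trial enrols open repair only. The same sentence attributes the deaths to systemic inflammation and multi-organ failure, and Protocol 8.5.1 treats efficacy against multi-organ failure as measurable only after 36 hours. So 30-35% can reasonably be read as a survivor rate. On that reading, 37% is 2 points above the range, and power at 35% is 76-78% against 79%. The protocol states its effect as a 22-point difference, and at a 30-35% survivor rate that scale keeps power above 80%. The conditioning on 36-hour survival is also visible, because Protocol 8.2 gives the exclusion immediately before sizing the evaluable patients. Finally, SAP 6 says only that 129 was not reached; it does not attribute low power to any single cause.

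**Conclusion.** No change to the plan. The sample-size arithmetic is right for its inputs, and the implied 46.5% is compatible with two of the three figures in Protocol 1.1. The third is too loosely defined to contradict it. The possible loss of power at 30-35% is anywhere from about 2 to 34 points against 79% with the relative risk or odds ratio held, and there is a gain with 22 points held at a 30-35% survivor rate. That spread comes from the choice of reading, not from a demonstrated mistake. The re-evaluation and blind review in Protocol 8.2 and 8.6 were suitable ways to deal with an uncertain event rate.

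What remains is a missing citation and label, a gap in justification that a reader can fill with one line of arithmetic. The planning rate enters no analysis: the adjusted odds ratio and its interval come from observed data. Recruitment has ended, and comparing the observed pooled rate with the planned one in about 35 patients would tell a reader almost nothing. The conclusion rests on equal early deaths by arm for the 46.5%, and on the documents giving no definition of the 30-35%.

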8.3 BASELINE CHARACTERISTICS AND DISPOSITION

As per Section 6.4., the baseline assessments consist of those assessments carried out in the screening period and those carried out prior to the first dose of the study medication on D0.

Demographic and baseline characteristics are summarised by treatment group and overall.

Disposition and reasons for discontinuation are summarised for all patients together with treatment exposure and study duration by treatment group.

8.4 Evaluation of safety

All patients who receive a minimum of one administration of study medication are included in the safety analysis.

Adverse Events

Treatment Emergent Adverse Effects (TEAEs) and SAEs are classified according to the Medical Dictionary for Regulatory Activities (MedDRA) SOC and the preferred term. The incidence of these events will be summarised by treatment group in tables which will also include information on severity and relationship to study medication. These summaries will be based on the Safety Set. The frequency of complications is summarised by treatment groups in terms of counts.

Vital Signs

Vital signs data (BP, HR and temperature) is summarised by treatment group separately at D0, D1, D2, D3, D4, D5, D6, D9, D13 and D30. The maximum change from baseline over the 30-day follow-up period will be calculated for each patient and summarised.

Vital signs summaries will be in terms of mean, median, standard deviation (SD), minimum and maximum.

Clinical Laboratory Parameters

Descriptive statistics (mean, median, SD, minimum and maximum) for biochemistry and haematology will be obtained and tabulated by treatment group at D0, D1, D2, D3, D4, D5, D6 and D30. Descriptive statistics (mean, median, SD, minimum and maximum).

Shift tables (within, below and above the normal range) will also be provided for each parameter in relation to the maximum change from baseline from D0 over the complete 30-day follow-up period.

8.5 Evaluation of efficacy

8.5.1 *Evaluation of primary efficacy endpoint*

The primary endpoint of the study will be:

- All-cause mortality at D30

To be eligible for efficacy analysis each patient must receive at least two doses of the study medication with an effect time of 12 hours after second dose. This means that a death within 36 hours from the first dose of study treatment leads to exclusion from efficacy analysis. This derives from the fact that based on the prior clinical phase I/II studies with interferon beta-1a, its effect on the expression of CD73 and production of adenosine will require 12 to 24 hours from administration of the drug. Thus, therapeutic levels will not be reached until 12 hours from the second dose, i.e. 36 hours from the first dose. Measuring efficacy against multi-organ failure prior to this point is misleading because therapeutic levels have not yet been reached.

The efficacy analyses will be conducted using logistic regression model for the observed mortality rates in the two treatment groups. Stratification factors used in the randomisation will be included in the model. Primary result will be presented as an adjusted odds ratio and a 95% CI for the adjusted odds ratio. Also, a 95% confidence interval (CI) for the difference in the observed mortality rates will be calculated. A two-sided significance level of 0.05 will be used for all analyses.

There will additionally be an evaluation of the homogeneity of the treatment effect by investigating treatment by centre and treatment by baseline factor interactions in the logistic model. Data for the primary efficacy endpoint will also be presented for key, pre-defined subgroups of patients together with 95% CIs for the difference in those rates to supplement the investigation of homogeneity. Mortality at D30 will be illustrated also using survival function and Kaplan-Meier curves including log-rank test as an exploratory analysis.

8.5.2 *Evaluation of secondary efficacy endpoints*

By way of further confirmatory measures of efficacy, the following endpoints will be analysed:

- Time and reason/diagnosis of death up to D90 (3 months)
- Number of VFDs up to D30
- Number of days receiving hemodialysis at D30 and D90
- Number of ICU free days up to D30
- Organ failure free days up to D30
- Neutralizing antibodies IFN beta (NAbs) in whole blood samples up to D30
- Number of days in hospital up to D30 and D90 (length of stay in another health care facility)
- Prevalence of abdominal compartment syndrome, i.e. intra-abdominal pressure (IAP) value differences between study groups
- Disability on D90 measured by modified ranking scale (mRS)

All-cause mortality at D90 (3 months) will be compared using methods for the evaluation of time to event endpoints. Hazard ratios for each of these time periods will be presented with associated 95% CIs and log-rank p-values for the FAS. Also, similar logistic regression model than for the primary endpoint (D30 mortality) will be done.

For endpoints number of VFDs, number of ICU free days, organ failure-free days, number of days on hemodialysis, IAP values data will be summarised in terms of the mean, median, minimum and maximum, and the treatment groups will be compared using the Mann-Whitney U-test. Complete data on organ failure free days may be unavailable due to SOFA scores not being assessed after ICU treatment. To account for this, the number of organ failure free days will be analysed by expressing these as a proportion of the days on which SOFA scores are available. Disability measured with mRS will be summarized descriptively and the treatment groups will be compared using the Cochran-Mantel-Haenzel test.

All secondary analyses are designed to be supportive of the analysis of the primary endpoint and there will be no adjustments for the multiplicity of endpoints so that each analysis will be undertaken at the two-sided 5% level of significance.

8.6 INTERIM ANALYSIS

An interim analysis will be performed after there are 1) at least 31 and 2) 84 patients that are eligible for the primary efficacy endpoint analysis (excluding early deaths within 36 hours from first dose of study treatment, similarly than for primary analysis). At this point the study can be stopped for efficacy or futility depending on the interim analysis results. The first interim is brought further up as the recruitment rate has markedly stagnated, mainly due to changes in treatment practices of RAAA. The sample size calculations will be re-evaluated after the first interim.

Primary efficacy endpoint will be evaluated using O'Brien and Fleming criteria controlling the type I error rate. If the study goal is reached, the study can be stopped early for efficacy. The first interim analysis focuses mainly for the futility stopping, as the power is low to reach the efficacy criteria. The power to reach the study goal at the second interim analysis with 84 evaluable patients is approximately 40%, but also this calculation will be re-evaluated after the first interim.

In addition, there will possibility to stop the study for futility at the interim analyses. Predefined criteria for futility stopping will be defined in the interim analysis plan.

Statistical analysis plan for the final and interim analysis will be prepared before the interim analysis. A blind review of data will be performed before the interim analysis to confirm analysis assumptions for e.g. overall number of events.

